**Funding Source:**

This work was supported by a developmental grant to [name] from the Roybal Center for Dementia Caregiving Mastery at Emory University (P30AG064200 – Co-Directors, [name] and [name]) funded by the National Institute on Aging at the National Institutes of Health.

## **Background and Rationale**

Nationwide, over 11 million Americans, mostly family members and friends, provide informal unpaid care to millions of persons living with dementia. As the population ages, these numbers are expected to rise exponentially alongside dementia's deleterious impact on public health and accompanying social and financial costs. Informal care partners play a critical role in the quality of life and care of persons living with dementia and influence their ability to age in place at home rather than relocating to costlier and less preferred formal long-term care settings (e.g., assisted living, nursing homes). Yet, caregiving in the context of dementia frequently involves burden, stress, and emotional strain, all of which negatively influence caregivers' overall health, well-being, self-care abilities, and mortality. Such outcomes compromise caregiving and ultimately negatively affect care recipients, including their ability to remain at home. Needed are interventions that bolster informal care partners' ability to succeed in their care roles and minimize negative outcomes.

## **List of Specific Aims**

1. To refine the program, "Improving Care through Improv" for informal dementia care partners.
2. To assess the feasibility, acceptability, and preliminary efficacy of "Improving Care through Improv" through pilot testing

## **Brief Description of Project Design**

- Phase 1 involves refining the training program, "Improving Care through Improv" (Aim 1).
- Phase 2 involves piloting the training program with 40 adult informal care partners of person with moderate dementia to test its effect on self-perceived caregiving mastery through a no-control, pre-post design single-group trial with three time points: baseline; immediately upon completion, and 3-months post baseline (Aim2). The intervention will be delivered to up to 5 groups of 8 to 12 participants each. All groups will be exposed to the same in-person training during weekly 2-hour sessions held over a 4-week period. At 3-months post baseline, there will be a 90-minute in-person session to allow for completion of the assessment and to obtain participant feedback.

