## **Procedures/Human Subjects Involvement**

Study participants will be exposed to the same in-person group training delivered by study personnel during weekly 2-hour sessions held over a 4-week period. In addition to the four in-person training sessions, participants will be invited to attend a final one-and-a-half hour in-person group meeting, which will involve completion of the 3-month post baseline assessment and invite feedback on the overall intervention experience through

open-ended questions. Participants will complete a self-administered pen and paper survey at all three study time points: baseline; upon training completion; and 3-months post baseline. At baseline, we will collect care partners' demographic details (e.g., age, gender, race, ethnicity, employment status, education, urban/suburban/rural status, relationship to care recipient), and key information pertaining to their caregiving history, experiences, and care recipient.

At all three time points, participants will be asked to complete measures to assess: caregiver mastery, self-perceived stress, anxiety, caregiver burden, and perceived changes in care recipients' behavioral expressions and with associated care partner distress. We also will ask participants to assess their care recipients' quality of life. Participants will complete these self-administered surveys in person with researchers present to answer any questions. The surveys collected at baseline and upon training completion will be distributed and completed at the first and fourth training sessions, respectively.

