### **Inclusion Criteria**

Eligible participants will be: 1) 18-years or older; 2) actively engaged in the care of community-dwelling persons living with moderate dementia (4 or 5 on a 7-point dementia-staging scale) who is not likely to be institutionalized within the next 6 months; 3) able to attend at least 3 of the 4 in-person sessions. Participants also will need to be able to read, write, and communicate in English. Screening will take place over the phone when potential participants reach out to the study team and express interest in the study.

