### **Data Analysis Plan**

Descriptive statistics will be calculated for all demographics and instrument scores at baseline, completion, and three months after baseline. Internal reliability will be assessed using Cronbach's alpha at baseline. Missingness will be assessed and corrective measures used as appropriate (multiple imputation). Repeated measures analysis of variance will be used with dependent variables across the three time points. Error rate adjustments (Bonferroni or Dunn-Sidak tests) will be made due to the implementation of multiple comparisons across dependent variables. Effect sizes will also be computed and assessed for clinical significance. The percentages of caregivers whose scores improve or decline from baseline to completion and post-completion assessments will be calculated. IBM SPSS for Windows, version 24.0 will be used to perform computations.

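### Does a no-control pilot that says it will test an effect, and reports the percentage who improve, risk presenting chance as benefit?

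*Combined protocol and SAP*

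**What the plan says.** The Brief Description of Project Design sets out a pilot in 40 care partners "to test its effect on self-perceived caregiving mastery through a no-control, pre-post design single-group trial with three time points". The List of Specific Aims is more modest: "To assess the feasibility, acceptability, and preliminary efficacy of" the programme, through pilot testing.

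The Data Analysis Plan lists descriptive statistics for all instrument scores at baseline, completion and three months, and repeated measures analysis of variance across the three times. It adds Bonferroni or Dunn-Sidak adjustment across dependent variables. It goes on: "Effect sizes will also be computed and assessed for clinical significance". Then: "The percentages of caregivers whose scores improve or decline from baseline to completion and post-completion assessments will be calculated". No minimum change is set for improvement or decline, and no interval is mentioned. Cronbach's alpha is computed at baseline but is not tied to any threshold.

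The Benefits & Risks section says that signs of efficacy would lead the team to seek funding for further tests and, ideally, scale-up.

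**The concern.** Two features look wrong together.

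First, testing an effect claims more than a single-group pre-post comparison can deliver. Changes in the care situation, repeated surveying and the survey setting ("Participants will complete these self-administered surveys in person with researchers present to answer any questions") all enter the change score along with the training.

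Second, the improve percentage counts any upward movement, however small. Ordinary fluctuation alone puts a sizeable share of caregivers in that category. With no reference rate, a statement that a large minority or about half improved could be read as the share helped by the training, and could feed the decision to seek further funding when mean mastery had not moved.

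**Working it through.** The documents name no mastery instrument and give no range, SD, reliability, tie rate, alpha level or expected improvement rate. There is no planned figure to reproduce. From the documents: n = 40, three time points, no control. Everything else below is assumed.

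**1. Share improved when the mean does not move.** If changes are symmetric about zero, P(improve) = (1 - P(unchanged))/2.

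| Unchanged scores (assumed) | Expected improved | Expected declined |
|---|---|---|
| 0% | 50% | 50% |
| 10% | 45% | 45% |
| 20% | 40% | 40% |
| 30% | 35% | 35% |
| 40% | 30% | 30% |

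Simulated integer scores (1,000,000 pairs per setting, retest correlation 0.5 to 0.9) gave 32% down to 18% improved at an SD of 1 point, 40% to 30% at SD 2, 46% to 41% at SD 5, and 48% to 46% at SD 10. A figure of 40-50% is therefore conditional on the scale. Coarse or very stable scales give less.

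**2. Sampling spread at n = 40.** If the true rate is 50%, the central 95% of observed rates is 14 to 26 of 40 (35-65%), and P(at least 24 of 40) = 0.134. If the true rate is 40%, the range is 25-55%.

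**3. What a modest gain looks like.** With no ties, a mean gain of d SD and retest correlation r, P(improve) = Phi(d / sqrt(2(1 - r))). For d = 0.3:
- r = 0.5: Phi(0.3/1.000) = 0.618 improved, 1 - 0.618 = 0.382 declined, a gap of 0.236.
- r = 0.7: Phi(0.3/0.775) = 0.651 improved, 0.349 declined, a gap of 0.302.

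With no mean change the expected gap is zero whatever the tie rate. The pair of percentages is informative where the improved share alone is not. The unchanged share is 100% minus the two planned percentages.

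**4. What else would reveal a null.** With no mean change, a valid test at an assumed two-sided 0.05 level is non-significant 95% of the time even before the planned adjustment. The descriptive scores and effect sizes would sit near zero change.

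**5. Would a cut-off help?** The obvious candidate uses the planned alpha: count a change only beyond 1.96 x SD x sqrt(2(1 - alpha)). For alpha 0.7, 0.8 and 0.9 this is 1.518, 1.240 and 0.877 SD. The share labelled improved at zero mean change is then:

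| | alpha 0.7 | alpha 0.8 | alpha 0.9 |
|---|---|---|---|
| r = 0.5 | 6.4% | 10.8% | 19.0% |
| r = 0.7 | 2.5% | 5.5% | 12.9% |

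The nominal 2.5% per tail is met only where alpha equals r. At alpha 0.8, a real 0.3 SD gain shows as 17.4% improved and 6.2% declined (r = 0.5), or 11.3% and 2.3% (r = 0.7). The rule still labels up to 19% improved when nothing moved, and it hides most of a modest gain. Alpha measures internal consistency on one occasion; it does not measure stability between occasions.

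**6. Attribution.** If non-specific drift were 0.2, 0.3 or 0.5 SD of change (assumed), a two-sided 0.05 paired test at n = 40 would be significant with probability 0.23, 0.46 or 0.87. That limit belongs to the single-group design. Rewording the purpose as estimating change would not alter it.

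**The case for a change.** The best case for a change is that funding depends on signs of efficacy that the plan never defines. It gives no threshold for improvement, no criterion for clinical significance and no interval on the effect size. A 0.3 SD gain yields 62-65% improved, which lies within the 35-65% that chance allows at n = 40, so the percentage barely distinguishes a modest gain from none. Even 30% improving with nothing changed would mislead without a reference. Replacing the testing language, adding intervals and reporting three categories would cost almost nothing.

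Most of this stands as a comment on reporting. The improve percentage is weak evidence alone, and an interval on mean change would be a better summary. What does not stand is that the plan, followed as written, would produce a wrong result. The percentage is one descriptive line among outputs that address the mean directly, and decline is reported next to improve. The next step named in Benefits & Risks begins with further tests, so a positive signal would not be treated as proof. The wording about testing an effect carries its own qualification in the same sentence.

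**Conclusion.** No change to the plan is needed. The single-group design is a fair trade-off for a pilot aimed at feasibility, acceptability and preliminary efficacy, and the plan says openly that there is no control. Any-change percentages can reach 50% improved with no mean change, and exceed 40% only if fewer than 20% of scores are unchanged. This rests on symmetric changes and on tie rates the documents do not give. The planned decline percentage, scores by time point, adjusted repeated measures analysis and effect sizes would already show an unmoved mean.

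The available remedies add little to the plan itself. The unchanged share follows by subtraction. A confidence interval and a sentence on attribution are things analysts would sensibly supply when writing up. The alpha-based cut-off trades one distortion for another. The improved share should not be read as the share helped by the training, but that caution belongs to interpretation of the results.

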## **Procedures/Human Subjects Involvement**

Study participants will be exposed to the same in-person group training delivered by study personnel during weekly 2-hour sessions held over a 4-week period. In addition to the four in-person training sessions, participants will be invited to attend a final one-and-a-half hour in-person group meeting, which will involve completion of the 3-month post baseline assessment and invite feedback on the overall intervention experience through

open-ended questions. Participants will complete a self-administered pen and paper survey at all three study time points: baseline; upon training completion; and 3-months post baseline. At baseline, we will collect care partners' demographic details (e.g., age, gender, race, ethnicity, employment status, education, urban/suburban/rural status, relationship to care recipient), and key information pertaining to their caregiving history, experiences, and care recipient.

At all three time points, participants will be asked to complete measures to assess: caregiver mastery, self-perceived stress, anxiety, caregiver burden, and perceived changes in care recipients' behavioral expressions and with associated care partner distress. We also will ask participants to assess their care recipients' quality of life. Participants will complete these self-administered surveys in person with researchers present to answer any questions. The surveys collected at baseline and upon training completion will be distributed and completed at the first and fourth training sessions, respectively.

Three months post baseline, we will reconvene the group and distribute the final survey and invite feedback on the feasibility and accessibility of the intervention. This session will be 90 minutes long. Researchers will take detailed fieldnotes to capture the content of the group discussion, especially their feedback on their intervention experiences. Participants will take part in the training program, "Improving Care through Improv." The training builds care partner skills cumulatively over a series of four classes, each with a separate focus: (1) Yes, and....: Actively listening and observing and offering and accepting interactions; (2) Being in the moment: Meeting people where they are and committing to what is happening; (3) How to collaborate: Give, take, and making your partner look good; (4) Giving up control: Accepting failure, pivoting, being flexible, leaning into uncertainty, and expecting the unexpected. All classes are highly interactive and invite informal caregiver to engage with the instructors and one another. The first class (Yes, and...), will begin with introductions, which will allow instructors and participants to gain familiarity and comfort with one another and share their care situations and experiences. The subsequent three classes (Being in the moment; How to collaborate; and Giving up control), will begin by inviting participants to reflect on the previous week, including care experiences and any attempts to use improv with their care recipients. Each week, an icebreaker exercise will follow opening discussions. Next, the instructors will provide an overview of the weekly topic and illustrate relevant skills through demonstration. Then, they will introduce and teach relevant improv exercises, which will allow participants to model and apply skills, first with the trainers and then amongst other caregivers. Feedback and coaching will follow each exercise. The final 20 minutes of each 2-hour class will be devoted to review, reflection, and group discussion, including how improv skills could be applied to their caregiving

situations. The first and fourth training sessions will involve an additional 30 minutes on top of the 2-hour training to complete paperwork/surveys. During all training sessions as well as the 90-minute three-months post baseline sessions, researchers will engage in participant observation. A detailed observation guide will facilitate observation during all group sessions. Researchers will observe and document in fieldnotes, what transpires, who is involved, what participants do, say, and how they respond to the instructors and one another, as well as their reactions to the materials and exercises. Researchers also will audio record each group session. These recordings will not be transcribed but be available for researcher reference.

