### **Number of Participants**

Up to 50 participants will be recruited for the pilot test.

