enrolled on an ongoing basis. Pilot testing will begin with the first group once we have recruited at least 8 participants. Research staff will clearly explain the requirements of the study prior to enrollment, obtain several contact avenues (phone numbers, email), and will work with participants as we schedule training sessions to identify days of the week/times of day that might be most convenient. If necessary, we are unable to recruit a sample of 40 participants through the IMCC, we will submit an IRB protocol amendment to expand our recruitment plan through other organizations and sites. At the recommendation of the advisory team (Aim 1) and ongoing recruitment feedback, we will expand recruitment to allow the flyers and newsletter information to be shared through by advisory team members, researchers, and participants, including snowball sampling. In the process of recruiting potential participants are asking if they may share the information with their peers. We also realize that flyers are posted and electronic communications are sent, they can be shared with others. We wish to include persons not directly recruited through the Emory's memory care clinic but who fit study criteria. In order to further expand recruitment, we wish to advertise on social media through the Gerontology Institute social media accounts with links to a webpage about the project hosted on the Gerontology Institute website. The website will include information from the recruitment flyer.

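### Acceptability is an aim, but overall feedback is solicited only in the 3-month group session, with no structured or private measure and no route for people who do not attend

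*Combined protocol and SAP*

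**What the plan says.** The List of Specific Aims sets the second aim as "To assess the feasibility, acceptability, and preliminary efficacy of 'Improving Care through Improv' through pilot testing". The Brief Description of Project Design plans for "piloting the training program with 40 adult informal care partners", and Number of Participants allows a higher ceiling: "Up to 50 participants will be recruited for the pilot test".

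The feedback is placed at the end of follow-up. The design summary says that at three months "there will be a 90-minute in-person session to allow for completion of the assessment and to obtain participant feedback". Procedures/Human Subjects Involvement repeats this: "we will reconvene the group and distribute the final survey and invite feedback on the feasibility and accessibility of the intervention". The same section says participants are invited to this meeting, that the questions are open-ended, and that "Researchers will take detailed fieldnotes to capture the content of the group discussion".

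The survey measures listed for the three time points are mastery, stress, anxiety, burden, the care recipient's behavioral expressions with the related distress, and the care recipient's quality of life. On how the surveys are completed, the section says "Participants will complete these self-administered surveys in person with researchers present to answer any questions".

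The section also provides for guided observation of all four training classes, with fieldnotes on what participants say and how they react to the content, and audio recordings that will not be transcribed. The Data Analysis Plan covers instrument scores only.

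**The concern.** An acceptability finding should describe the people who started the program. Here the only direct request for an overall opinion comes about two months after the last class, at a meeting people may choose not to attend. Those who disliked the program are plausibly less likely to come. Those who do come are apparently asked in a group, with peers and study staff present. Selection and courtesy both push towards a favourable answer.

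The plan also names no acceptability variable. It therefore cannot report what share of starters found the program acceptable, and multiple imputation, planned for missing data, has nothing to impute on this question. Under Benefits & Risks the sponsor says it will seek further funding and scale up if there are signs of efficacy. Whether people who begin the program find it acceptable matters directly to that decision.

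**Working it through.** **Comparison of the text.** The plan states no retention, approval or acceptability figure, so there is nothing to reproduce. The check is whether any planned source gives acceptability among starters.

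- *Three-month session.* It reaches attenders only. The format is open-ended and recorded in notes. The text says feedback covers feasibility and accessibility; acceptability is not named there.
- *Surveys at the three time points.* No acceptability or satisfaction item is listed.
- *Observation at the four classes.* It reaches everyone who attends a class, including people who later leave. It takes place in the group with researchers present. It does not give one response per person, and it cannot cover reasons for leaving that arise after the last class attended.
- *Class discussions.* These concern the previous week's care experiences and how improv skills apply to caregiving. Rating the program is not described as part of them.
- *Leavers.* Phone and email details are collected before enrollment (Participants and Recruitment), but no exit contact is described.
- *Data Analysis Plan.* It gives no analysis of feedback or fieldnotes and no acceptability proportion.

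No source yields a rate among starters.

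**Illustration of size.** The number starting, N, is 40 or 50, from the protocol. Non-return of 10%, 20% or 30% and approval near 90% among returners are assumptions. With f favourable returners and m non-returners:

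- lowest possible approval among starters = f / N
- highest possible approval among starters = (f + m) / N
- width of the range = m / N, which is the non-return share

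| N | Non-return | Among returners | Lowest | Highest |
|---|---|---|---|---|
| 40 | 10% (4) | 32/36 = 89% | 32/40 = 80% | 36/40 = 90% |
| 40 | 20% (8) | 29/32 = 91% | 29/40 = 72.5% | 37/40 = 92.5% |
| 40 | 30% (12) | 25/28 = 89% | 25/40 = 62.5% | 37/40 = 92.5% |
| 50 | 10% (5) | 40/45 = 89% | 40/50 = 80% | 45/50 = 90% |
| 50 | 20% (10) | 36/40 = 90% | 36/50 = 72% | 46/50 = 92% |
| 50 | 30% (15) | 32/35 = 91% | 32/50 = 64% | 47/50 = 94% |

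A single scenario within these ranges, with N = 40, assumes that 90% of returners and 40% of non-returners approve:

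- 20% non-return: (0.9 × 32 + 0.4 × 8) / 40 = 32/40 = 80%, against 90% among returners
- 30% non-return: (0.9 × 28 + 0.4 × 12) / 40 = 30/40 = 75%, against 90% among returners

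The plan does not intend to report any such proportion. The figures show only how far the opinion of returners could differ from that of starters.

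**The case against.** The strongest reply is that acceptability is assessed throughout. A reader might infer from the three-month arrangement that all acceptability information comes from those who came back. The documents do not support that. Researchers use an observation guide at every class, record what participants say and how they react, and keep the audio for reference. Each class ends with 20 minutes of review and discussion. Across sessions, these notes cover everyone who attended at least once, so they do not share the selection problem of the final meeting. That part of the reply stands. What remains is that the observations are not private, cannot explain absence, and give no proportion.

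Second, non-return may be low. Participants receive $75 for each session, including the last, scheduling takes account of their convenience, and eligibility requires being able to attend at least three of the four classes. This is fair. The size of the problem is unknown, and the illustration is only as good as its assumptions.

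Third, a qualitative assessment is a legitimate choice in a small single-group developmental pilot. That also stands, and it is why the point is an improvement rather than a fault that undermines the study. The spoken format is itself an inference: open-ended questions could be answered in writing, although the reference to notes on a group discussion suggests otherwise.

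**Conclusion.** The point holds in a limited form. Direct feedback on the whole program is solicited once, from those who attend the three-month session. The plan names no structured or private acceptability measure and describes no route for people who do not attend. It therefore cannot state acceptability among starters, and its conclusion is likely to lean favourable.

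A reader might go further and say that upward bias is established. It is not: the documents give no retention or approval figure, and the direction rests on the reasonable assumption that dissatisfied people return less often or speak less freely. Under the assumed case of 40 starters, 8 non-returners and 29 of 32 returners approving, approval among starters is known only to lie between 72.5% and 92.5%. If fewer people fail to return, the range narrows in proportion.

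**What to change.** A cheap improvement, in four parts:

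1. Add four to six fixed-response acceptability items to the session 4 paper survey, which already has 30 extra minutes set aside for paperwork. Have them completed privately and returned in a sealed envelope with instructors out of the room. Questionnaires carry participant codes, so describe this as confidential, not anonymous.
2. Send the same items by email or phone, using contact details already held, to anyone who stops attending or misses session 4. An eligible participant may miss that session, so this step is needed for the denominator. Answers given to study staff by phone may still be polite ones.
3. Report the proportion finding the program acceptable among all who attended at least one session, with the number not responding, a 95% CI, and best-case and worst-case bounds for non-responders. The interval alone does not cover non-response, and a simple binomial interval ignores clustering within up to five groups, so show the counts by group as well.
4. Keep the three-month discussion and the fieldnotes as qualitative support.

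The cost is about one page on an existing survey, a few emails or calls, and an IRB wording amendment. The downside is a slightly longer survey and probably a less favourable figure.
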